**Analysis of secondary outcomes (Secondary Aim 2):**

The secondary outcomes of clinical remission as assessed by the CDAI, PRO2, PRO3 reduction of hsCRP by >50% and to <5 mg/L, reduction of FCP by >50% and to a value of <250mcg/g and combined clinical remission and resolution of inflammation will be analyzed using the same methods described for the primary outcomes.

The secondary outcomes of fatigue, sleep quality, social aspects and pain interference will be measured using PROMIS short forms using the same methods as previously employed within CCFA Partners. PROMIS items are calibrated using a T score such that 50 is the mean for the general US population with a standard deviation of 10. Higher scores reflect greater level of the domain. We will compare PROMIS scores at baseline and at the end of the trial using a t-test. If there are meaningful differences in baseline scores between the treatment arms, comparison of the PROMIS measures at the end of follow-up will be adjusted for the baseline value using linear regression.

**Analysis of data from weeks 7 – 12 (Secondary Aim 3):** After week 6, participants will need to provide for the meals on their own if they choose to remain on the diet. This provides an opportunity to further assess the combined feasibility of the diets in the real world and patients' satisfaction with following the diet. Utilizing results from 24-hour dietary recalls, we will determine the proportion of patients assigned to each arm who elect to remain on the diet through week 12. We will also determine the proportion of patients who were able to discontinue steroid use by week 12 among the subgroup who were taking steroids in weeks 1-6. Finally, we will assess reasons for discontinuation of the diet among those who did not continue. Comparisons will be made using the CMH test following the principle of intention to treat. The analysis will be repeated among the subgroup of participants who achieved remission by week 6. These results will be qualitatively compared to the free text data on satisfaction and personal experience with the diets.

**Change from baseline stratified by treatment arm:** For continuous outcome measures, such as sCDAI, PRO2, PRO3, and FCP, we will compare the week 6 and week 12 values to the baseline value using the Wilcoxon sign rank test, a nonparametric paired test. These analyses will be conducted separately for each treatment group. Imputation of missing data for this analysis will assume the worst case scenario that the outcome measure was worse during follow-up than at baseline. (Note that approach to missing data for other analyses are described below).

**Approach to missing data (PCORI Methodology Standard MD1-5):** Our study design will minimize missing data by requiring participants to continue to provide data and samples in order to continue to receive the study diets without cost. In addition, we will employ reminder methods that were developed in our current CCFA Partners RCT and will collect symptoms daily, but have documented that less frequent data collection is adequate. It is possible that missing follow-up data will be more common among participants who did not have reduced symptoms, particularly those whose symptoms worsened. There are several approaches to missing data in clinical trials. Complete case analysis violates the principle of

intention to treat and as such will not be employed. For continuous measures, last observation carried forward (LOCF) is the most commonly used, but it is not necessarily the most conservative. Baseline observation carried forward (BOCF) may be more appropriate, particularly in circumstances where the outcome would be expected to return to the baseline level if the treatment is discontinued. The European Medicines Agency recommends picking the most conservative approach depending on the individual trial, favoring a responder analysis (i.e. converting continuous variables to dichotomous variables) and categorizing all dropouts as treatment failures. We will use this approach in analyses for aims 1 and 2. For the continuous variables in the secondary outcomes, we will use BOCF as the most conservative approach. Sensitivity analyses will compare results of our BOCF analysis with that obtained using LOCF or multiple imputation methods. All results will be interpreted and reported after taking into account the results of the sensitivity analyses, applying the principle put forth by the EMA to not favor the “experimental” arm, which in this RCT would be the SCD.

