### **7.3 Current Symptoms**

Participants' current symptoms, both Crohn's disease-related and otherwise, will be collected at each visit. Crohn's symptoms will also be collected through daily online surveys. Patient reported outcomes using PROMIS and other measures will be assessed at each visit.

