#### **8.4.2 Efficacy Analysis**

Analysis of the primary outcome: The primary analyses for the RCT will use 2-sided tests of statistical significance and will be performed using the intention-to-treat principle. Thus, patients will be classified according to the study arm that they were assigned, regardless of the amount of food from the assigned diet consumed. The primary analysis will compare the proportion of patients who achieve a symptomatic remission (aim 1) at week 6 using the Cochran-Mantel-Haenszel (CMH) chi square test, which is equivalent to the score test derived from the conditional logistic regression. All patients who are withdrawn or lost to follow-up prior to week 6 will be considered treatment failures. The MSD will be considered the reference group for all analyses. Although randomization should minimize unbalance between the groups, it is still possible that unbalance may occur. As such, we will use stratified analyses and logistic regression analysis to adjust for potential unbalance between the two groups as observed in

the descriptive analyses. Age, sex, smoking status, duration of CD, presence of disease involving the colon and/or rectum, use of corticosteroids during the trial, current use of biologic therapy, and current use of immunomodulator therapy will be examined individually for potential confounding of the main outcome using logistic regression analysis. All variables that affect the crude estimate of the relative risk of effectiveness by 10% or greater will be included in the final model.

Stratified analyses will be used to assess for treatment effect heterogeneity based on the following variables: presence of documented inflammation at baseline (defined as FCP>250 mcg/g, hsCRP >5 mg/L). Although pre-specified, we have not powered the study for these subgroup analyses and as such they will be considered hypothesis generating. Therefore, we will report the overall results as well as results for each subgroup. We note that the strongest a priori hypothesis for treatment effect heterogeneity is with the presence or absence of inflammation. We hypothesize that the SCD may appear relatively more effective among those patients without active inflammation than among those with confirmed active inflammation at baseline.

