## 5.2. Sample size

The study is designed to enroll 97 patients into each of the treatment arms. Specific aims 1 and 2 will be considered separately and no reduction in type 1 error will be applied for multiple testing. The anticipated remission rate in the group receiving the MSD is unlikely to exceed 40% given the historical remission rates in placebo arms of Crohn's disease trials and assuming only a modest therapeutic benefit of this less restrictive of the two diets. Sample size calculations assume no loss to follow-up since all participants who are lost to follow-up will be categorized as non-responders in the analyses of both dichotomous primary outcomes (symptomatic remission and reduction in mucosal inflammation). Our PPRN Patient Governance Council met and determined that the minimum clinically important difference in remission rates is 20% as smaller differences are unlikely to justify the challenges of following a strict restriction diet such as the SCD. Thus, we used an anticipated remission rate of 40% with the MSD and 60% with the SCD to determine the sample size. With 97 participants per group, the study will have 80% power with a type 1 error of 5% to detect a difference of 40% vs 60% in effectiveness of the two diets using a chi test.

In reality, we anticipate that the remission rate in the MSD will be less than 40%. The power curve shown below depicts the power to detect a 20% difference based on the remission rate in the MSD arm of the trial where  $p_1$  represents the remission rate in the SCD arm (i.e.,  $p_1=0.3$  represents power to detect a difference of 10% vs 30% across a sample size ranging from 60 to 120). With 97 participants per group, there is more than 90% power to detect a difference of 10% vs 30% and 80% power to detect a difference of 40% vs 60%.

Finally, all of the power estimates are likely slight under estimates. We expect even more power when the Cochran-Mantel-Haenszel (CMH) chi test is used since we expect that the odds ratios in different strata are in the same direction.

Viewed alternatively, with 97 participants per arm, there is 80% and 90% power to detect the following differences based on the effectiveness of the control diet (i.e. the MSD).

Proportion of MSD group achieving the outcome	80% power to detect an absolute difference (SCD - MSD) greater than or equal to	90% power to detect an absolute difference (SCD - MSD) greater than or equal to
10%	15%	18%
20%	18%	21%

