#### **5.5.3. Analysis of PROMIS and arthritis measures**

PROMIS measures will be compared at baseline, week 6 and week 8 using a t-test or with adjusted linear regression if there is evidence of confounding despite randomization. Additional analyses will compare change in PROMIS measures from baseline to week 6 and week 12 between groups. The RADAI arthritis screen, RAPID3, and BAS-FI will be treated as a continuous measures and compared between groups similar to the approach for PROMIS.

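### For outcomes measured only at visits, LOCF is a weak week-6 check on BOCF, yet the plan allows it to be the only check

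*Combined protocol and SAP*

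**What the plan says.** **The missing-data rule.** Protocol 8.4.2 (Approach to missing data) makes BOCF the main method for continuous secondary outcomes and adds: "Sensitivity analyses will compare results of our BOCF analysis with that obtained using LOCF or multiple imputation methods". SAP 5.5.2 repeats this. Both say that all results will be read in the light of these sensitivity analyses, so as not to favor the SCD. Both also expect missing data to be more frequent among participants whose symptoms did not improve.

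**When the outcomes are measured.** Protocol 7.3 states: "Patient reported outcomes using PROMIS and other measures will be assessed at each visit". The schedule in protocol 6.1 and the follow-up table in SAP section 4 place PROMIS and the joint measures at weeks 0, 6 and 12. Protocol 7.6 gives the same times for hsCRP.

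**What is compared.** Protocol 8.4.2 and SAP 5.5.2 compare PROMIS at baseline and at the end of the trial. SAP 5.5.3 adds: "Additional analyses will compare change in PROMIS measures from baseline to week 6 and week 12 between groups". It treats the RADAI screen, RAPID3 and BASFI in a similar way. Protocol 8.2 offers mean hsCRP as a possible outcome.

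**Withdrawal.** Under protocol 6.5 and 6.2.5, randomized participants who withdraw should have an end-of-study visit that includes PROMIS, joint symptoms and hsCRP. Those who stop the diet for reasons other than worsening disease are asked to attend the next scheduled visit.

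**Outcomes under other rules.** For the primary outcome: "All patients who are withdrawn or lost to follow-up prior to week 6 will be considered treatment failures". The within-arm change analyses of sCDAI, PRO2, PRO3 and FCP use a separate worst-case rule.

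**The concern.** A sensitivity analysis is useful only if its assumption about the missing values differs from that of the main analysis. With no measurement scheduled between baseline and week 6, the last observation of a participant who disappears in that interval is the baseline observation. LOCF and BOCF then make the same assumption about that person.

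Unequal loss is plausible here. The trial is open label, and protocol 1.4 describes the MSD as much the easier diet to follow. If one arm loses more participants, BOCF pulls that arm's mean further back towards baseline, and at week 6 LOCF would largely agree. Since the plan makes interpretation depend on this check, an agreement that is partly built in could be reported as robustness.

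**Working it through.** **1. The design figure.** Inputs from protocol 8.4.2 and SAP 5.2: two-sided test, type 1 error 5%, power 80%, 40% vs 60%, 97 per arm. With pooled variance and no continuity correction:

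n = [1.960 × √(2 × 0.5 × 0.5) + 0.842 × √(0.4 × 0.6 + 0.6 × 0.4)]² / 0.20² = (1.386 + 0.583)² / 0.04 ≈ 97 per arm.

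The stated figure reproduces. It supplies no loss rate: "Sample size calculations assume no loss to follow-up since all participants who are lost to follow-up will be categorized as non-responders". Every loss rate below is therefore an assumption.

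**2. Value imputed for a visit-only measure (PROMIS, RADAI, RAPID3, BASFI, mean hsCRP if used).**

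| Participant | BOCF | LOCF |
|---|---|---|
| Lost before week 6, no withdrawal visit: week-6 value | baseline | baseline (identical) |
| Lost before week 6, withdrawal visit made: week-6 value | baseline | withdrawal-visit value, if carried forward |
| Lost after week 6: week-12 value | baseline | week-6 value or a later withdrawal-visit value |

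The first row needs no assumption. In simulations with no withdrawal visits, the BOCF and LOCF data sets were identical in every run.

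**3. Size if loss is unrelated to outcome.** Let both arms truly improve by δ points, with loss proportions p(SCD) and p(MSD). Under BOCF an arm's mean improvement shrinks to (1 − p) × δ, so

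false difference (SCD − MSD) = [p(SCD) − p(MSD)] × δ.

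The simulation used 97 per arm, no true diet difference, SD 10 (the T-score SD in SAP 5.5.1.5) and a two-sided t-test at 5%, with 2,000 runs per scenario. Assumed: baseline mean 58, baseline to week-6 correlation 0.5 and no withdrawal visits. BOCF and LOCF gave the same results:

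| Loss MSD / SCD | δ | Formula | Simulated | Rejection rate |
|---|---|---|---|---|
| 10% / 10% | 5 or 8 | 0 | about 0 | 4.4% to 5.1% |
| 10% / 20% | 5 | 0.10 × 5 = 0.50 | 0.53 | 6.6% |
| 10% / 20% | 8 | 0.10 × 8 = 0.80 | 0.82 | 8.6% |
| 10% / 25% | 5 | 0.15 × 5 = 0.75 | 0.77 | 8.4% |
| 10% / 25% | 8 | 0.15 × 8 = 1.20 | 1.19 | 12.0% |
| 5% / 30% | 5 | 0.25 × 5 = 1.25 | 1.25 | 14.6% |
| 5% / 30% | 8 | 0.25 × 8 = 2.00 | 2.05 | 28.2% |

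A baseline-adjusted regression on observed cases, standing in for multiple imputation, gave about 0 points and 4% to 6% rejection. That is expected, because loss was simulated as random.

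**4. Effect of withdrawal visits.** Suppose a share v of lost participants attend and half of their change is visible by then (an assumption). The LOCF difference is then gap × δ × (1 − v/2). For 10% / 25% and δ = 8:
- v = 0.5: 1.20 × 0.75 = 0.90 (simulated 0.89, against 1.20 for BOCF).
- v = 1: 1.20 × 0.50 = 0.60 (simulated 0.59, against 1.18 for BOCF).

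Under that assumption LOCF reduces the difference but does not remove it.

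**5. The opposite assumption.** Take 20% vs 5% loss, with a 6-point improvement in those who stay and none in those lost. The true arm difference is now 0.15 × 6 = 0.9. BOCF gives 0.9, which is correct. Imputation within arm gives 0.0 and hides a real difference.

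**6. Daily measures.** sCDAI items are collected daily, so LOCF and BOCF can differ there. As an illustration, daily means of 4 stools, pain 1.5 and wellbeing 1.5 give 44 + 7 × (8 + 7.5 + 10.5) = 226. By week 4, values of 2, 0.8 and 0.8 give 44 + 7 × (4 + 4 + 5.6) = 139.2. However, the planned between-diet analyses of these symptom scores are responder analyses, and their continuous analysis follows the worst-case rule. BOCF therefore governs mainly the visit-only measures.

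**The case against.** The strongest reply is that the affected group is small by design. Withdrawing participants should attend a visit, those who stop the diet for other reasons are asked to stay until the next one, and free food depends on providing data. Multiple imputation is already named, and the analytic plan is to be agreed before the final analyses. Section 2 of the protocol calls the secondary aims exploratory. All of this stands and limits the importance of the point. It does not remove it: attendance cannot be guaranteed, the wording leaves the method open, and the plan does not say whether withdrawal-visit values are carried forward.

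A reader might draw four stronger conclusions that the documents do not support.

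- **That the check can only repeat the BOCF result.** Withdrawal visits give LOCF a different value, and at week 12 it can carry the week-6 value.
- **That the trial's main result is exposed.** Week-6 remission counts losses as failures, so neither BOCF nor LOCF touches it.
- **That BOCF is wrong and multiple imputation is right.** Step 5 shows the reverse can hold, and the plan itself expects loss to be linked to lack of improvement.
- **That the error would favor the SCD.** If the SCD arm loses more, BOCF makes the SCD look worse, in line with the stated principle. It would favor the SCD only if the MSD arm lost more.

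**Conclusion.** The point holds for continuous secondary outcomes measured only at visits, at week 6. There LOCF equals BOCF for every participant lost without a post-baseline visit and departs from it only through withdrawal visits, so on its own it tests little about unequal loss between diets.

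With loss unrelated to outcome, the unequal-loss scenarios gave false differences of about 0.5 to 2.05 T-score points and false-positive rates of 6.6% to 28.2%. The upper end needs a 25-point loss gap, and equal loss gives no bias. These figures rest entirely on assumed loss rates and improvements. Because the direction of the error turns on why people leave, the plan needs a check whose assumption differs from BOCF and can be varied. This is a worthwhile correction to secondary analyses and does not bear on the primary conclusion.

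**What to change.** In protocol 8.4.2 and SAP 5.5.2:

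1. Make multiple imputation the required sensitivity analysis at weeks 6 and 12. Impute within arm from baseline, biologic stratum and all observed follow-up, including withdrawal-visit values.
2. Keep LOCF as supplementary at most. If it is kept, name the measures and weeks it applies to, and say whether withdrawal-visit values are carried forward.
3. Add a delta or tipping-point version that shifts the imputed values over a stated range, in each arm separately. The range should at least reach the shift that returns lost participants to their baseline level, since the plan expects missingness to go with lack of improvement. Varying the arms separately tests the promise not to favor the SCD whichever arm loses more.
4. Report the number lost without any post-baseline visit, by arm, beside these results.

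The cost is a few lines of SAP text and a small amount of extra programming and reporting. No new data are needed.

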#### **8.4.3 Safety Analysis**

All subjects entered into the study and randomized at the baseline visit will have detailed information collected on adverse events for the overall study safety analysis.

#### **8.5 Subject Population(s) for Analysis**

As a comparative effectiveness study, the primary efficacy and safety analysis will use the principle of intention to treat such that all randomized patients will be included in the group that they were randomized to, regardless of the level of adherence with the assigned diet.

### **9 Safety and Adverse Events**

#### **9.2 Definitions**

##### **9.2.1 Adverse Event**

An **adverse event** (AE) is any symptom, sign, illness or experience that develops or worsens in severity during the course of the study. Intercurrent illnesses or injuries should be regarded as adverse events. Abnormal results of diagnostic procedures are considered to be adverse events if the abnormality:

- results in study withdrawal
- is associated with a serious adverse event
- is associated with clinical signs or symptoms
- leads to additional treatment or to further diagnostic tests
- is considered by the investigator to be of clinical significance

A **preexisting condition** is one that is present at the start of the study. A preexisting condition should be recorded as an adverse event if the frequency, intensity, or the character of the condition worsens during the study period.

##### **9.2.2 Serious Adverse Event**

###### **Serious Adverse Event**

Adverse events are classified as serious or non-serious. A **serious adverse event** is any AE that is:

- fatal
- life-threatening
- requires or prolongs hospital stay
- results in persistent or significant disability or incapacity
- a congenital anomaly or birth defect
- an important medical event (not life threatening but may require intervention; for example drug overdose, drug abuse, a seizure not resulting in hospitalization)

All adverse events that do not meet any of the criteria for serious should be regarded as **non-serious adverse events**.

### **9.2.3 Expected Adverse Events**

As a short term study of two diets, there are few expected risks of the two interventions. These include allergic reaction to a component of the food, intolerance of the food other than as an allergic reaction, and worsening of Crohn's disease manifested as any of the following: worsened abdominal pain, worsened diarrhea, bowel obstruction, penetrating complications such as fistula or abscess. In addition, worsening of extraintestinal manifestations of Crohn's disease is possible, such as worsening arthropathy, mouth sores, skin rashes including pyoderma gangrenosum and erythema nodosum, and ocular manifestations such as episcleritis or uveitis. The Crohn's disease related adverse events would not be considered to be caused by the diets, but rather as a consequence of failure of the diet based therapy to induce disease remission. Some exacerbations of Crohn's Disease may result in hospitalization and/or the need for surgery. In rare circumstances, exacerbations of Crohn's disease may be life-threatening.

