### **6.3 Rescue Therapy [if applicable]**

Participants will remain under the care of their treating gastroenterologist while in the study. If their symptoms worsen, participants will contact their treating gastroenterologist and follow any recommendations with regard to changes in therapy for their Crohn's disease. Participants whose worsening symptoms require a change in the current treatment for Crohn's disease will be considered study treatment failures and will be withdrawn from the study. See Section 6.5 for subject withdrawal information.

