### **9.3 Recording of Adverse Event (AE)**

At each contact with the subject from the screening visit to the end of study visit, the Site Investigator or Site Coordinator will seek information on adverse events by specific questioning and, as appropriate, by examination. Information on all adverse events will be recorded immediately on the AE case report form (CRF). The clinical course of each event will be followed until resolution, stabilization, or until it has been determined that the study intervention or participation is not the cause.

Related, treatment-emergent serious and severe adverse events that are still ongoing at the end of the study period will be followed up to determine the final outcome, which may include resolution or stable outcome.

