### **9.4 Relationship of AE to Study**

The relationship of each adverse event to the study procedures should be characterized by the Site Investigator and recorded on the case report form. The relationship to the study intervention will be classified as definitely related, possibly related, not related, or unknown. For reporting purposes, an Adverse Event is considered "related to participation in the research" if the cause of the event is deemed possibly related or definitely related to the investigational product or a procedure that was performed for the purposes of the research.

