### **9.5 Reporting of Serious Adverse Events and Unanticipated Problems**

A Serious Adverse Event or Unanticipated Problem (see definition below) is required to be reported to the relying IRB within 10 days. If the adverse event involved a death and indicates that participants or others are at increased risk of harm the investigators are required to submit a report to the relying IRB within 3 days.

Non-medical Unanticipated Problems that should be reported to the IRB may include complaint of a participant when the complaint indicates unexpected risks or the complaint cannot be resolved by the research team, breach of confidentiality, incarceration of a participant when the research was not previously approved under Subpart C and the investigator believes it is in the best interest of the subject to remain on the study, or premature completion of the entire study for any reason.

Serious Adverse Events or Unanticipated Problems will be reported to the relying IRB using either a Reportable Event form from the relying IRB, or by writing a narrative including the minimum necessary information listed below. If not all information is known within the reporting timeframe, the site investigator should still complete a Reportable Event form or narrative within the timeframe with the information available and inform the relying IRB that a follow-up report will be provided when all information is known.

- Study identifier
- Study Center
- Subject number
- A description of the event
- Date of onset
- Current status
- Whether study intervention was discontinued
- The reason why the event is classified as serious
- Investigator assessment of the association between the event and study intervention

If an event does not meet the definition above of a Serious Adverse Event or Unanticipated Problem, a narrative summary of events that occurred should be submitted to the relying IRB at the time of Continuing Review, including a rational for why the event(s) was not reportable within 10 days.

Any known serious adverse event that occurs after the study period and is considered to be possibly or definitely related to the study intervention or study participation will be recorded and reported to the PI, the sponsor, and the relying IRB immediately.

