#### **9.5.1 Follow-up SAE report**

If an SAE has not resolved at the time of the initial report and new information arises that changes the investigator's assessment of the event, a follow-up report including all relevant new or reassessed information (e.g., concomitant medication, medical history) should be submitted to the relying IRB. The site investigator is responsible for ensuring that all SAEs are followed until either resolved or stable.

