### **12.2 Risks**

The intervention in this trial poses little risk to participants. The prescribed diets are consistent with many dietary recommendations to minimize consumption of “processed” foods. There is a theoretical risk of delaying a change in the patient’s medication regimen while trying the study diets. However, the duration of the primary intervention period is only 6 weeks and we will exclude patients who are hospitalized for their CD, require in excess of 20mg per day of prednisone or the equivalent, or for whom the treating physician believes that surgery will be required within 6 weeks. There is minimal risk of phlebotomy, including bruising or fainting. However, nearly all of these patients would be expected to undergo phlebotomy for clinical reasons at the same time.

As with all research, there is the risk of loss of confidentiality of the data. Within the clinical trial, all data collected will be collected in a manner consistent with Good Clinical Practice. The case report forms (CRFs) will be electronic, avoiding the risk of paper forms. Access to the data will be limited to the research team, including the investigators, the research coordinator, and the data analysts. Electronic data will be

stored on servers within the University of North Carolina. Access to the server is password protected. The servers are backed-up nightly to prevent loss of information.

No vulnerable populations are included in this study.

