### 2.2. Expected Adverse Events

As a short term study of two diets, there are few expected risks of the two interventions. These include allergic reaction to a component of the food, intolerance of the food other than as an allergic reaction, and worsening of Crohn's disease manifest as any of the following: worsened abdominal pain, worsened diarrhea, bowel obstruction, penetrating complications such as fistula or abscess. In addition, worsening of extraintestinal manifestations of Crohn's disease is possible, such as worsening arthropathy, mouth sores, skin rashes including pyoderma gangrenosum and erythema nodosum, and ocular manifestations such as episcleritis or uveitis. The Crohn's disease related adverse events would not be considered to be caused by the diets, but rather as consequence of failure of the diet based therapy to induce disease remission.

These risks are specified in the protocol and informed consent form.

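### Relatedness of Crohn's worsening is fixed in advance in one section and judged per event in another, and SAEs that start after withdrawal for worsening may go uncollected

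*Combined protocol and SAP*

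**What the plan says.** **Causality.** Protocol 9.2.3 lists worsening of Crohn's disease, including obstruction, fistula and abscess, among the expected risks of the two diets. It accepts that exacerbations can lead to hospital admission or surgery and, rarely, threaten life. It then states: "The Crohn's disease related adverse events would not be considered to be caused by the diets". Appendix C 2.2 says the same: "would not be considered to be caused by the diets, but rather as consequence of failure of the diet based therapy". Section 9.4 (and Appendix C 2.4) asks for an individual judgement: "The relationship of each adverse event to the study procedures should be characterized by the Site Investigator". Section 12.2 names a harm of taking part rather than of the food, a "theoretical risk of delaying a change in the" patient's medication.

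**Follow-up.** Section 9.3 (and Appendix C 2.3) follows each event to resolution, to stabilisation, or "until it has been determined that the study intervention or participation is not the cause". For serious and severe events still open at the end of the study period, it continues follow-up only if they are related. Section 9.5.1 (and Appendix C 2.5.1) sets no such condition: "The site investigator is responsible for ensuring that all SAEs are followed until either resolved or stable".

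**After the study period.** Section 9.5 (and Appendix C 2.5) covers "Any known serious adverse event that occurs after the study period and is considered to be possibly or definitely related to the study intervention"; the sentence then adds study participation as an alternative to the intervention.

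**Withdrawal.** Under 6.3, participants whose worsening requires a change of Crohn's treatment "will be considered study treatment failures and will be withdrawn from the study"; 6.5 agrees. Section 6.2.5 places the end-of-study visit at withdrawal, and 9.3 asks about adverse events only up to that visit.

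**Analysis.** Section 8.5 bases the safety analysis on all randomised patients. SAP 5.5.4 compares the proportion of patients with any SAE between arms by Fisher's exact test.

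**The concern.** A site cannot both treat relatedness of a Crohn's event as settled and assess it event by event. The answer has consequences, because two follow-up rules and one reporting rule depend on it.

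The statistical stake is the any-SAE comparison. It has no relatedness filter, but it can count only events that were collected. The participants whose collection ends early are those whose disease worsened enough to need a treatment change, so the length of observation depends on outcome. By contrast, 6.5 asks a participant who stops the diet for other reasons to stay in follow-up until the next scheduled visit.

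**Working it through.** The documents state no figure to reproduce. The check is to take a Crohn's-worsening event that a site treats as unrelated under 9.2.3 and apply each rule to it.

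1. *Recording during the study.* Section 9.3 records all adverse events whatever the cause. Nothing is lost.
2. *Reporting an SAE during the study.* Section 9.5 sends it to the IRB and 9.5.2 to the sponsor, neither with a relatedness condition. Section 9.6.2 sends SAE reports to the DSMB chair. Nothing is lost.
3. *Following an SAE that began during the study.* Section 9.3 could release it and, at the end of the study period, exclude it as unrelated. Section 9.5.1 requires follow-up until it is resolved or stable. The sections contradict each other, but the SAE is not simply dropped.
4. *Following a Crohn's event that is severe but not serious.* Section 9.3 could release it, and 9.5.1 does not apply because the event is not an SAE. No other section restores follow-up. **Gap (a).**
5. *An SAE that starts after withdrawal for worsening.* Sections 6.3 and 6.5 withdraw the participant, 6.2.5 puts the end-of-study visit at that point, and 9.3 stops asking about adverse events there. Section 9.5.1 concerns SAEs already reported and does not make the site look for a new one. If the study period ends at withdrawal, only the post-study rule in 9.5 remains. That rule needs the SAE to be known and to be judged possibly or definitely related to the intervention or participation. **Gap (b).**

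*Length of gap (b).* For withdrawal at week t, the time without inquiry is 12 − t weeks. At t = 3 this is 12 − 3 = 9 of 12 weeks.

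*Effect on the comparison.* SAP 5.5.4 counts patients, so a participant who already had an SAE by withdrawal is counted. What can be missed is a first SAE between withdrawal and day 84. Let w be the proportion of an arm withdrawn for worsening, and s the proportion of those who have such an SAE uncollected. With 97 per arm, the expected undercount is 97 × w × s in each arm, and the distortion of the difference in proportions is w₁s₁ − w₂s₂. With s similar in the two arms, the undercount is larger where w is larger. The documents give neither w nor s.

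**The case against.** The strongest reply is that the safety system does not run on the causality field. SAEs during the study are recorded and reported without regard to cause. Appendix C section 3 has the principal investigator review every SAE report in real time and the DSMB review all reported adverse events. DSMB reports are coded by treatment group (10.3.2), and SAP 5.5.4 applies no relatedness filter. All of this stands. A reader might infer that the most serious named risks drop out of follow-up, or that the DSMB and IRB could not see a diet signal. The documents do not support either inference: hospitalised and life-threatening events during the study meet the SAE definition, and 9.5.1 keeps them in follow-up.

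Second, 9.2.3 rules only on the diets, whereas the clauses in 9.3 and 9.5 also cover participation. The advance ruling therefore does not by itself satisfy the stopping condition in 9.3 or close the post-study route in 9.5. This also stands, with a limit. Section 9.4 defines relation to participation through the investigational product or a research procedure, and the delayed medication change in 12.2 does not clearly fit either.

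Third, *study period* is undefined, and ending it at individual withdrawal is an inference. A flare still open at withdrawal might also be followed under 9.3 until it resolves or stabilises, so a later admission could come to light. Both points are fair. They make gap (b) conditional, and they show that the text leaves the matter to each site.

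Fourth, the shortened observation comes from the withdrawal and end-of-study rules, not from the causality sentence. This is correct: removing that sentence alone would not lengthen observation.

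**Conclusion.** The point holds in a limited form. The documents contradict themselves on whether relatedness of Crohn's worsening is fixed or judged per event, and on whether SAE follow-up depends on relatedness. Beyond that there are two gaps: follow-up of Crohn's events that are severe but not serious, and collection of SAEs that start after withdrawal for worsening that requires a treatment change.

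The second gap assumes that the study period ends at the withdrawal visit. Its effect on the arm comparison further assumes that such withdrawals differ between arms and that some later SAEs go unrecorded. On those assumptions, the any-SAE comparison of all randomised patients rests on unequal observation and may understate SAEs in the arm with more worsening. The size cannot be computed from the documents. A count of withdrawn participants would not supply it, because it counts people leaving observation and not SAEs missed.

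This is an inexpensive improvement to the plan. It does not show that safety monitoring during the study fails.

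**What to change.** 1. In 9.2.3 and Appendix C 2.2, remove or reword the advance ruling, so that relatedness, including to participation, is judged case by case under 9.4 and Appendix C 2.4.
2. Reconcile 9.3 and Appendix C 2.3 with 9.5.1 and Appendix C 2.5.1, so that follow-up of SAEs does not depend on relatedness. State whether the same applies to Crohn's events that are severe but not serious.
3. Define the study period as running to planned day 84 for every randomised participant. After withdrawal, record SAEs to that day regardless of relatedness, by one call or chart check with the participant's consent, and count them in SAP 5.5.4.

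**Cost.** Wording changes, plus one contact or chart check per withdrawn participant. As an illustration only, if 5% to 20% of the 194 were withdrawn for worsening (an assumption; the documents give no rate), that is 0.05 × 194 ≈ 10 to 0.20 × 194 ≈ 39 contacts over the whole trial. Somewhat more events will be recorded or classed as possibly related.
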